5.1.1 Clinical indication for total thyroidectomy

5.1.2 Euthyroid (TSH at screening  $> 0.45 < 4.5$  mIU/mL)

5.1.3 Indication to total thyroidectomy for benign goiter or thyroid cancer not requiring suppressive thyroid hormone therapy

5.1.4 Age 18-89 years of age

5.1.5 Males and females

## **5.2 Exclusion Criteria**

A potential subject who meets any of the following exclusion criteria is ineligible to participate in the study.

- 5.2.1 Weight <50 or >150 Kg;
- 5.2.2 Graves' disease
- 5.2.3 Use of thyroid hormone therapy use of thyroid hormone therapy or thyroid supplements (at screening) except for multinodular goiter;
- 5.2.4 Indication for thyroid hormone suppressive therapy following surgery
- 5.2.5 Uncontrolled arterial hypertension. (Stage 2 or greater on medication); (>140/90 mmHg at screening while on medication (patients with hypertension controlled by therapy will be allowed to participate)).
- 5.2.6 Cardiovascular disease: congestive heart failure; unstable coronary artery disease (angina, coronary event, or revascularization within 6 months); atrial fibrillation, arrhythmia or ventricular arrhythmia,
- 5.2.7 Pregnancy, breastfeeding, or planned pregnancy within six months from the thyroidectomy
- 5.2.8 History of major depression or psychosis;
- 5.2.9 Uncontrolled diabetes (HbA1c > 8% or fructosamine < 325 mcmol/l in substitution of HbA1c to reflect recent improvement in diabetes control at screening
- 5.2.10 Conditions that in the opinion of the PI may impede the successful completion of the study

Patients on statin treatment will be allowed to participate in the study and the treatment will remain unchanged throughout the study.

## **6 STUDY ENTRY AND WITHDRAWAL PROCEDURES**

### **6.1 Study Entry Procedures**

#### **6.1.1 Required Pre-Registration Screening Tests and Procedures**

The study participants will be recruited primarily among patients attending the multidisciplinary endocrine tumor program at VCU, although self-referral from ClinicalTrials.gov will be allowed. The study will also be publicized among local endocrinologists and ENT surgeons. Self-referral will be allowed.

During the screening visit, the following procedures will be performed: informed consent, history and physical examination performed by a trained physician, weight and vital signs recorded by a trained physician or nurse.

#### Registration Process

After obtaining informed consent and all initial screening visit procedures, patients will participate in one screening visit, one dose adjustment outpatient visit, and three inpatient overnight admissions (referred as phenotyping visits)

### **6.2 Study Withdrawal Procedures**

- 6.2.1 A patient is free to withdraw from the study for any reason, at any time, without reason for doing so and without any penalty of prejudice.
- 6.2.2 A patient may be removed from treatment for one of the following criteria:
- 6.2.3 The study physician thinks it is necessary for the health and safety of the patient.
- 6.2.4 Principal Investigator's decision to discontinue the study.
- 6.2.5 The patient is non-adherent with the protocol
- 6.2.6 If an adverse event (including worsening of the concomitant illness) develops which is considered by the Investigator as incompatible with continuation of the study
- 6.2.7 Administrative reasons that require the patient to withdrawal
- 6.2.8 If pregnancy develops
- 6.2.9 Lost to follow-up
- 6.2.10 Patient death
- 6.2.11 All available data will be collected if feasible. The reason for discontinuation should be documented in the case report form (CRF).

If a patient decides to withdraw from the study, any information and specimens already collected will be handled according the following algorithm. Patients who withdrew consent before the end of their involvement will not have their data used.

**Table 2: Effects of Withdrawal on Data Collected.**

Timing of Withdrawal	Action
After the screening visit, before baseline	Data collected will not be deleted, but no additional information regarding the patient will be obtained.
After the baseline visit before 6 week Visits	Data collected will not be deleted, but no additional information regarding the patient will be obtained. Information gathered can still be used in analyses.
After the 6 week Visit before Month 3	Data collected will not be deleted, but no additional information regarding the patient will be obtained.
After Month 3 Visit before 6 Month	Data collected will not be deleted, but no additional information regarding the patient will be obtained.

## **7 PREMATURE TERMINATION**

**7.1** The sponsor has the right to terminate the trial prematurely if there are any relevant medical or ethical concerns, or if completing the trial is no longer practicable. If such action is taken, the reasons for terminating the trial must be documented in detail. All trial subjects still under treatment at the time of termination must undergo a final examination, which must be documented.

## **8 TREATMENTS**

### **8.1 Investigational /non Investigational Products**

The following medications will be used in this study:

- Levothyroxine (LT4)
- Liothyronine (LT3)
- Placebo (sugar pill)  
(Medisca empty gelatin capsules size 00 manufactured by CapsuleDepot)

The VCU Investigational Drug Pharmacy will over-encapsulate the Investigational Pharmacy will over-encapsulate LT4 plus placebo, or LT4 plus 5 mcg LT3 in "AM" and "PM" color coded capsules.

The pharmacy will create the over-encapsulating tablets and making matching placebo capsule placebo distinguish the AM and PM doses. They will use; dextrose, USP (anhydrous) manufactured by Medisca empty gelatin capsules size 00 manufactured by CapsuleDepot. The placebo capsules is used to assist in the blinding process. It will allow that two capsules to be given as one of the randomized study drug is one drug Levothyroxine alone. The placebo will make the number of capsules (2) the same dose Levothyroxine and Lithothyroxine dose combination.

## 8.2 Study Dosing Group

In this study, Levothyroxine (LT4) and placebo (a look-alike inactive substance, a “sugar pill”) will be compared to Liothyronine/levothyroxine (LT3/LT4) combination therapy. Levothyroxine (LT4) and Liothyronine (LT3) are drugs approved by the U. S. Food and Drug Administration (FDA).

There will be thirty (30) subjects enrolled into the study. They will be randomly assigned 1:1 into one of two study-dosing groups:

**Table 3: Randomization Dosing Table**

Study Group	Number of Subjects
LT4 group + Placebo	Fifteen Subjects
LT4/LT3 group	Fifteen Subjects

## 8.3 Dosage and administration

### Study Dosing

Patients in the LT4 group will be started at a dose of 1.6 mcg/Kg (52), while patients assigned to LT4/LT3 group will have 25 mcg of LT4 substituted with 5 mcg LT3 twice daily, to mimic the average daily T3 production form the thyroid (36). For patients taking oral Semaglutide the initial levothyroxine dose will be reduced to 1.2 mcg/Kg (-25 mcg in case of randomization to the levothyroxine/liothyronine group) to correct for increase in absorption. The VCU Investigational Pharmacy will over-encapsulate LT4 plus placebo, or LT4 plus 5 mcg LT3 in “AM” and “PM” color coded capsules. Patients will be instructed to take the AM drug first thing in the morning with water only, and to wait at least 30 minutes before taking other medications coffee or breakfast. The PM dose will be taken at least 30 minutes before dinner. Dose adjustments will be performed at the 6-week and 3-month follow up visits by an unblinded endocrinologist ([name]) aiming to achieve and maintain a target TSH within the normal range and within  $\pm 0.5$  mIU/ml from the baseline (pre-surgery) TSH, according to the scheme in Table 1. Doses will be rounded to the nearest available formulation. No changes will be made in LT3.

Patients and their healthcare providers will be encouraged to inform the study team of any change in medications. An information card containing a basic description of the protocol, study medications, and contact information of the PI and study coordinator will be given to the study. **participants with instructions to show it at any encounter with healthcare providers for the duration of the study.**

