## **9 STUDY PROCEDURES**

### **STUDY VISIT PROCEDURES**

The entire protocol consists of five visits: one screening visit, one baseline visit, one dose adjustment visit, and three inpatient overnight admissions (referred as “phenotyping visits”). The follow up study visits will occur in a +/- 7-day window. Study participants will be admitted for their baseline phenotyping visit before surgery. Randomization will be performed at the time of the baseline visit. On discharge from the hospital, (postoperative day 1 or 2) patients will start the study drugs. An outpatient visit for dose adjustment will occur six weeks following surgery. Three months after surgery, patients will have a second overnight phenotyping visit and therapy adjustment. A third phenotyping visit (end of study) will be performed six months after surgery. The overnight phenotyping visits will be identical, except no DXA scan will be performed at baseline and during the 6-month post-op visit.

The summary of the procedures is presented in the table 2 (study scheme)

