### 2.3 Dosing in Specific Patient Populations

#### 1.3.3 Primary Hypothyroidism in Adults and in Adolescents in Whom Growth and Puberty are Complete

Start LEVO-T at the full replacement dose in otherwise healthy, non-elderly individuals who have been hypothyroid for only a short time (such as a few months). The average full replacement dose of LEVO-T is approximately 1.6 mcg per kg per day (for example: 100 to 125 mcg per day for a 70 kg adult).

Adjust the dose by 12.5 to 25 mcg increments every 4 to 6 weeks until the patient is clinically euthyroid and the serum TSH returns to normal. Doses greater than 200 mcg per day are seldom required. An inadequate response to daily doses of greater than 300 mcg per day is rare and may indicate poor compliance, malabsorption, drug interactions, or a combination of these factors.

For elderly patients or patients with underlying cardiac disease, start with a dose of 12.5 to 25 mcg per day. Increase the dose every 6 to 8 weeks, as needed until the patient is clinically euthyroid and the serum TSH returns to normal. The full replacement dose of LEVO-T may be less than 1 mcg per kg per day in elderly patients.

In patients with severe longstanding hypothyroidism, start with a dose of 12.5 to 25 mcg per day. Adjust the dose in 12.5 to 25 mcg increments every 2 to 4 weeks until the patient is clinically euthyroid and the serum TSH level is normalized.

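### Section 8.3 starts elderly patients, and any with stable coronary disease who enrol, at full replacement, although the appended levothyroxine labels advise a lower start

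*Combined protocol and SAP*

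**What the plan says.** Section 8.3 gives the starting rule: "Patients in the LT4 group will be started at a dose of 1.6 mcg/Kg". The combination arm has 25 mcg of that LT4 replaced by LT3 5 mcg twice daily, "to mimic the average daily T3 production form the thyroid". There is one exception: "For patients taking oral Semaglutide the initial levothyroxine dose will be reduced to 1.2 mcg/Kg", again less 25 mcg in the combination arm. It corrects for absorption and has nothing to do with age or the heart.

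Section 9 sets the timing: "On discharge from the hospital, (postoperative day 1 or 2) patients will start the study drugs", and "An outpatient visit for dose adjustment will occur six weeks following surgery". A second adjustment follows at 3 months. Table 4 limits each change in dose to 10% or 20% according to TSH, and 8.3 holds LT3 fixed throughout.

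On eligibility, 5.1.4 reads "Age 18-89 years of age". Section 5.2.6 excludes heart failure, arrhythmia and "unstable coronary artery disease (angina, coronary event, or revascularization within 6 months". It does not mention stable coronary disease.

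The labels in Appendices B, C and D treat about 1.6 mcg/kg/day as average full LT4 replacement. On who may begin there, Appendix B (2.3) says: "Start LEVO-T at the full replacement dose in otherwise healthy, non-elderly individuals who have been hypothyroid for only a short time". The same section gives a much lower start for elderly or cardiac patients and says an elderly patient's full dose may be under 1 mcg/kg/day. The geriatric sections (8.5) repeat the advice to begin below full replacement.

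**The concern.** An eligible 80-year-old and a healthy 30-year-old of the same weight get the same start. The protocol's own appendices separate these two patients, and 8.3 gives no reason for treating them alike. Its dose rationale is general: thyroidal T3 output in 8.3 and a pharmacokinetic model in 2.1.

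What is at stake is safety early in treatment. Section 5.1 of the LT4 labels links over-treatment with angina and arrhythmia and singles out elderly patients and those with cardiovascular disease. If an elderly patient's true requirement is below 1 mcg/kg, a 1.6 mcg/kg start is more than a quick route to the right dose, because it overshoots that dose.

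No sample size, power or alpha figure depends on this point.

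**Working it through.** Inputs: starting doses, the fixed LT3 dose and the 1.2 mcg/kg tier from 8.3; percentage steps from Table 4; visit timing from Table 1 and Section 9; the elderly requirement from 2.3 of the LT4 labels. A 70 kg patient is used for illustration, before rounding to available tablets. Table 4's percentages are applied to LT4 only, because LT3 does not change.

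1. **Is the start full replacement?** 1.6 × 70 = 112 mcg/day. The label's own example for 70 kg is 100 to 125 mcg, so yes. In the combination arm, 112 − 25 = 87 mcg LT4 plus 2 × 5 = 10 mcg LT3. With the protocol's exchange of 10 mcg LT3 for 25 mcg LT4, that is 87 + 25 = 112. With the ratio in Appendix E (25 mcg LT3 to about 100 mcg LT4), it is 87 + 40 = 127. Either way the combination arm also starts at full replacement.

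2. **When can it change?** 42 ± 7 days gives 35 to 49 days after surgery, then again at 3 months.

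3. **How far down can titration go?** The largest cut, 20%, applies only if TSH is below 0.1.
   - LT4 arm: 1.6 × 0.8 = 1.28 mcg/kg after 6 weeks; 1.28 × 0.8 = 1.02 mcg/kg after 3 months.
   - Combination arm at 70 kg: 87 × 0.8 × 0.8 = 55.7 mcg LT4. Adding 25 for the fixed LT3 gives 80.7, or 80.7 / 70 = 1.15 mcg/kg LT4-equivalent. With the Appendix E ratio it is 95.7 / 70 = 1.37.

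   A patient who needs less than 1 mcg/kg can therefore still be above requirement after both maximal cuts.

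4. **What would the 1.2 mcg/kg tier do?**
   - LT4 arm: 1.2 × 70 = 84 mcg, a fall of 28/112 = 25%. One maximal cut gives 1.2 × 0.8 = 0.96 mcg/kg, below 1 at the first adjustment.
   - Combination arm: 84 − 25 = 59 mcg LT4 (28/87 = 32% less LT4) with LT3 still 10 mcg. With the protocol's exchange, 59 + 25 = 84, matching the LT4 arm. Both arms drop by the same 28 mcg whichever exchange is used.

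5. **How reversible is a start that proves too low?** With TSH above 7.0, Table 4 adds 20% at each visit.
   - LT4 arm: 84 × 1.2 = 100.8 mcg after 6 weeks, still 10% below 112; 100.8 × 1.2 = 121 mcg after 3 months.
   - Combination arm: 59 × 1.2 × 1.2 = 85 mcg LT4 against a full start of 87.

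**The case against.** The best answer is that these patients differ from those the label's cautious start has in mind. They are euthyroid at entry, keep their thyroid until surgery and start drug a day or two later. The trial is continuing replacement, and the label attaches cardiac harm to over-treatment, not to replacement as such. This stands as a reason not to use the labels' 12.5 to 25 mcg start, which could badly under-replace someone newly without a thyroid. It does not rescue a full start in the elderly. The labels already allow for recent hypothyroidism, and even then they confine the full start to people who are healthy and not elderly.

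The second answer is the existing safeguards: the exclusions in 5.2.5 and 5.2.6, investigator discretion in 5.2.10 and investigator approval in Section 5, endocrinologist-run screening (10.2), an echocardiogram before any study drug (10.3.2), withdrawal under 6.2.3 and 6.2.6, and DSMB and cardiologist input (Section 12). These narrow the exposed group. But they act on entry or after an event, and none lowers the starting dose.

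Third, a lower tier carries its own risk of under-replacement. That is true, and it is the main price of the change.

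**Conclusion.** The point holds as a cheap patient-safety improvement of minor to moderate weight. For elderly patients the mismatch between 8.3 and the appended LT4 labels is direct, and Table 4 cannot fully undo it: the lowest reachable LT4 dose is about 1.02 mcg/kg, against a possible requirement under 1. For coronary disease the point is conditional. Eligibility of stable disease is inferred from the silence of 5.2.6, and because that criterion names angina the group may be small. The protocol gives no expected age or cardiac mix, so the number affected is unknown and may be 0 of 30.

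A reader might infer more than the documents support:

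- **That the trial overdoses these patients by 4.5 to 9 times** (112/25 and 112/12.5 at 70 kg). The label figure is a poor comparator for patients who were euthyroid until surgery.
- **That waiting about 6 weeks for a TSH check is itself a fault.** Section 2.4 of the LT4 labels recommends checking TSH 6 to 8 weeks after a dose change.
- **That LT3 should begin at 5 mcg once daily, as the LT3 labels advise for such patients.** Those steps are written for LT3 given alone. The difference is 5 mcg/day for 7 to 14 days, 35 to 70 mcg in total. Combined with the lower tier, it would leave the combination arm at 59 + 12.5 = 71.5 against 84 mcg LT4-equivalent, about 15% lower, for a negligible gain.
- **That the absence of uncorrected adrenal insufficiency from 5.2 is a gap of the same kind.** It is a label contraindication that the screening endocrinologists would apply in any case.

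**What to change.** In 8.3, extend the 1.2 mcg/kg starting tier to patients above a stated age (for example 65) or with known coronary disease. In the combination arm take 25 mcg off the LT4 and leave LT3 at 5 mcg twice daily. Apply the rule identically in both arms, from baseline characteristics only. The sponsor's clinicians should confirm the age and the dose, because the LT4 labels' dosing sections give no age cut-off.

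The amendment is short, and the pharmacy already handles this tier for semaglutide users. It needs no new capsule scheme, so the blind is unaffected. The cost is possible under-replacement in the few patients who need the full dose. It can outlast the 6-week visit and run through the 3-month phenotyping visit, where energy expenditure, a primary endpoint, is measured. The second adjustment can then restore the dose before the 6-month visit.

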### **9.10 DXA Scan (Dual-energy x-ray Absorptiometry):**

**DXA** stands for dual-energy x-ray absorptiometry (also known as a **DEXA scan**). A simple, 10-minute test takes a comprehensive snapshot of your exact breakdown of bone, fat tissue, and muscle mass. The DXA scan is the most accurate and precise body fat test available. There are not any special preparations needed, except to stop taking any calcium supplements for 24 hours before the test. Study participants are requested to lay still on a table while a sensor (similar to an X-ray machine) moves over the body from the head to the feet. Wear comfortable clothing. Study volunteers will undergo (DXA scan) at the baseline and six-month visits. The only potential risk associated with DXA scan is the exposure to radioactivity.

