**Table 2. Drugs That May Decrease T4 Absorption (Hypothyroidism)**

Potential impact: Concurrent use may reduce the efficacy of LEVO-T by binding and delaying or preventing absorption, potentially resulting in hypothyroidism.	
Drug or Drug Class	Effect
Calcium Carbonate Ferrous Sulfate	Calcium carbonate may form an insoluble chelate with levothyroxine, and ferrous sulfate likely forms a ferric-thyroxine complex. Administer LEVO-T at least 4 hours apart from these agents.
Orlistat	Monitor patients treated concomitantly with orlistat and LEVO-T for changes in thyroid function.
Bile Acid Sequestrants -Colesevelam -Cholestyramine -Colestipol Ion Exchange Resins -Kayexalate -Sevelamer	Bile acid sequestrants and ion exchange resins are known to decrease levothyroxine absorption. Administer LEVO-T at least 4 hours prior to these drugs or monitor TSH levels.
Other drugs: Proton Pump Inhibitors Sucralfate Antacids - Aluminum & Magnesium Hydroxides - Simethicone	Gastric acidity is an essential requirement for adequate absorption of levothyroxine. Sucralfate, antacids and proton pump inhibitors may cause hypochlorhydria, affect intragastric pH, and reduce levothyroxine absorption. Monitor patients appropriately.

**Table 3. Drugs That May Alter T4 and Triiodothyronine (T3) Serum Transport Without Affecting Free Thyroxine (FT4) Concentration (Euthyroidism)**

Drug or Drug Class	Effect
Clofibrate Estrogen-containing oral contraceptives Estrogens (oral) Heroin / Methadone 5-Fluorouracil Mitotane Tamoxifen	These drugs may increase serum thyroxine-binding globulin (TBG) concentration.
Androgens / Anabolic Steroids Asparaginase Glucocorticoids Slow-Release Nicotinic Acid	These drugs may decrease serum TBG concentration.

Potential impact (below): Administration of these agents with LEVO-T results in an initial transient increase in FT4. Continued administration results in a decrease in serum T4 and normal FT4 and TSH concentrations.
	
Salicylates (> 2 g/day)	Salicylates inhibit binding of T4 and T3 to TBG and transthyretin. An initial increase in serum FT4 is followed by return of FT4 to normal levels with sustained therapeutic serum salicylate concentrations, although total T4 levels may decrease by as much as 30%.

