### **17 PATIENT COUNSELING INFORMATION** Inform the patient of the following information to aid in the safe and effective use of

#### **LEVO-T:**

##### *Dosing and Administration*

- Instruct patients that LEVO-T should be taken with a full glass of water since the tablet may rapidly disintegrate.
- Instruct patients to take LEVO-T only as directed by their healthcare provider.
- Instruct patients to take LEVO-T as a single dose, preferably on an empty stomach, one-half to one hour before breakfast.
- Inform patients that agents such as iron and calcium supplements and antacids can decrease the absorption of levothyroxine. Instruct patients not to take LEVO-T tablets within 4 hours of these agents.
- Instruct patients to notify their healthcare provider if they are pregnant or breastfeeding or are thinking of becoming pregnant while taking LEVO-T.

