## **PATIENT COUNSELING INFORMATION**

**Inform the patient of the following information to aid in the safe and effective use of *levothyroxine sodium tablets*:**

***Dosing and Administration:***

- Instruct patients to take levothyroxine sodium tablets only as directed by their healthcare provider.
- Instruct patients to take levothyroxine sodium tablets as a single dose, preferably on an empty stomach, one-half to one hour before breakfast.
- Inform patients that agents such as iron and calcium supplements and antacids can decrease the absorption of levothyroxine. Instruct patients not to take levothyroxine sodium tablets within 4 hours of these agents.
- Instruct patients to notify their healthcare provider if they are pregnant or breastfeeding or are thinking of becoming pregnant while taking levothyroxine sodium tablets.

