**TABLE 1: DRUGS THAT MAY DECREASE T3 ABSORPTION (HYPOTHYROIDISM)**

Potential impact: Concurrent use may reduce the efficacy of liothyronine sodium by binding and delaying or preventing absorption, potentially resulting in hypothyroidism.	
Drug or Drug Class	Effect
Bile Acid Sequestrants -Colesevelam -Cholestyramine -Colestipol Ion Exchange Resins -Kayexalate -Sevelamer	Bile acid sequestrants and ion exchange resins are known to decrease thyroid hormones absorption. Administer Liothyronine Sodium to these drugs or monitor TSH levels.

**Table 2: Drugs That May Alter Triiodothyronine (T3) Serum Transport Without Affecting Free Thyroxine (FT4) Concentration (Euthyroidism)**

Drug or Drug Class	Effect
Clofibrate Estrogen-containing oral contraceptives Estrogens (oral) Heroin / Methadone 5-Fluorouracil Mitotane Tamoxifen	These drugs may increase serum thyroxine-binding globulin (TBG) concentration
Androgens / Anabolic Steroids Asparaginase Glucocorticoids	These drugs may decrease serum TBG concentration

Slow-Release Nicotinic Acid	
Salicylates (>2 g/day)	Salicylates inhibit binding of T4 and T3 to TBG and transthyretin. An initial increase in serum FT4 is followed by return of FT4 to normal levels with sustained therapeutic serum salicylate concentrations, although total T4 levels may decrease by as much as 30%.
Other drugs: Carbamazepine Furosemide >80 mg IV Heparin Hydantoins Non-Steroidal Antiinflammatory Drugs - Fenamates H	These drugs may cause protein binding site displacement. Furosemide has been shown to inhibit the protein binding of T4 to TBG and albumin, causing an increased free-T4 fraction in serum. Furosemide competes for T4-binding sites on TBG, prealbumin, and albumin, so that a single high dose can acutely lower the total T4 level. Phenytoin and carbamazepine reduce serum protein binding of thyroid hormones, and total and FT4 may be reduced by 20% to 40%, but most patients have normal serum TSH levels and are clinically euthyroid. Closely monitor thyroid hormone parameters

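### Section 8.3 sets one 30-minute minimum between the AM capsule and all other medications, without the 4-hour separation that the appended levothyroxine labels require for calcium and iron

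*Combined protocol and SAP*

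**What the plan says.** **Protocol body.** Section 8.3 has patients take the AM capsule on waking, with water, and then "to wait at least 30 minutes before taking other medications coffee or breakfast". The PM capsule is timed only against dinner. The other provisions on co-medication in that section are a lower starting dose for oral semaglutide users, an encouragement to report medication changes, and an information card to show to healthcare providers. None sets a separation interval, and Section 8.3 does not point to the appended labels.

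The only timing instruction for calcium in the body is in Section 9.10, where DXA preparation asks participants to "stop taking any calcium supplements for 24 hours before the test". Section 5.2 excludes no one for using calcium, iron or antacids.

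**Appended levothyroxine labels.** For calcium carbonate and ferrous sulfate, Appendix B, Table 2 says: "Administer LEVO-T at least 4 hours apart from these agents". Table 2 in Appendices C and D gives the same interval. Patient counselling in Appendix B names iron, calcium supplements and antacids, and continues: "Instruct patients not to take LEVO-T tablets within 4 hours of these agents". Appendices C and D match: "Instruct patients not to take levothyroxine sodium tablets within 4 hours of these agents". For antacids, Table 2 itself asks only for monitoring, so the 4-hour antacid interval rests on the counselling text.

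**The concern.** The protocol states one number for all co-medication, and for the calcium and iron products that its own appended labels single out, that number is too short. A participant can comply fully with Section 8.3 and still take the drug in a way the label advises against.

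What is at stake is LT4 absorption, and through it control of TSH, which Section 8.3 aims to hold within 0.5 mIU/ml of each patient's pre-surgery value. The protocol already treats absorption interactions as worth writing in: it cuts the starting dose for oral semaglutide because absorption rises. The reverse interaction, which the labels describe in patient-facing terms, has no counterpart in the body.

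**Working it through.** There is no sample-size or power figure to reproduce. The check sets the texts side by side and reads the visit schedule.

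1. **Intervals.** Section 8.3: at least 30 minutes. Labels: 4 h × 60 = 240 minutes. Difference: 240 − 30 = 210 minutes. Ratio: 30/240 = one eighth. Calcium or iron taken in those 210 minutes satisfies Section 8.3 and breaches the label.

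2. **Can both rules be met?** Yes. Section 8.3 gives a floor, so a patient who waits 4 hours meets both. The fault is an omitted specific rule, not an instruction to breach the label.

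3. **Is the longer rule elsewhere in the body?** No. Outside the appendices, no 4-hour separation is stated, and the Section 9.10 request concerns the scan.

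4. **What could detect or correct a loss of absorption?** The Schedule of Events places TSH at screening, baseline, 6 weeks, 3 months and 6 months, with dose adjustment at 6 weeks and 3 months only.
   - First correction: day 42 ± 7, that is day 35 to 49.
   - From the 3-month to the 6-month visit, taking these as days 91 and 182: 182 − 91 = 91 days. Shortest, with the 7-day windows: (182 − 7) − (91 + 7) = 77 days. Longest: (182 + 7) − (91 − 7) = 105 days.
   - A change in habit after month 3 could therefore go without a scheduled TSH for 77 to 105 days. This is a property of the visit schedule and applies to any late change, such as missed doses. It is not created by the 30-minute sentence.

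5. **What cannot be computed.** The documents give neither the number of users of calcium, iron or antacids nor the loss of absorption at 30 minutes. No effect in mcg, on TSH or on an endpoint can be derived.

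**The case against.** The best reply is that nothing here contradicts the label. Thirty minutes is a minimum, it agrees with the label's own interval of half an hour to an hour before breakfast, and the 4-hour rule is physically part of the protocol because the labels are appendices. A physician titrates each patient to their own baseline TSH, Medical History is scheduled at every visit, and Section 9.2 includes medication use. TSH follow-up is also a form of the monitoring that Table 2 asks for with antacids.

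Much of this stands and keeps the point minor. It does not remove it: Section 8.3 states a number for all other medications and sends no one to the appendices. The follow-up history is abbreviated, and reporting of changes is only encouraged and would not reveal the clock time of an unchanged calcium dose. Titration cannot remove irregular use, and nothing is scheduled between months 3 and 6.

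Two stronger readings are tempting. A reader might infer that patients are told only the 30-minute rule. The documents do not show that: the information card's text and the pharmacy's dispensing instructions are not included, and consent pages are not available for review. What can be said is that the visible protocol body lacks the 4-hour rule. A reader might also infer from Section 9.10 that the trial expects calcium users. That text is generic scan preparation; it allows for calcium use without indicating how common it will be.

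**Conclusion.** The point holds as a minor, cheap improvement. The textual mismatch is certain: 30 minutes against 240 for calcium carbonate and ferrous sulfate, and for antacids in counselling only. The consequence, reduced LT4 absorption in some patients, is possible on the labels' own account but unquantified.

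Four further inferences should not be drawn.

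- **Arm bias or endpoint effect.** Nothing in the documents shows that use would differ by arm, or that weight or energy expenditure would move.
- **Titration corrects most of a steady loss.** The 10% and 20% steps in Table 4 describe the titration scheme. Without the size of the loss, they do not show how much of it would be recovered.
- **The PM capsule is affected too.** This is unresolved. Section 8.3 can be read as placing LT4 in both capsules, while Section 8.1 suggests that placebo fills the second capsule in the LT4 arm: "The placebo will make the number of capsules (2) the same dose Levothyroxine and Lithothyroxine dose combination". If the PM capsule holds only LT3 or placebo, the calcium and iron rule does not reach it. The T3 absorption tables in Appendices F to H list other agents only; in Appendix H: "Bile acid sequestrants and ion exchange resins are known to decrease thyroid hormones absorption".
- **Bile acid sequestrants and resins are mishandled.** For these, Appendix B, Table 2 offers an alternative that the protocol's TSH schedule already provides: "Administer LEVO-T at least 4 hours prior to these drugs or monitor TSH levels".

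**What to change.** In Section 8.3 and on the information card, keep 30 minutes for food, coffee and non-interfering drugs, and add: *Take calcium, iron and antacids at least 4 hours apart from the AM capsule.*

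Ask the Investigational Pharmacy whether the PM capsule contains LT4 in either arm. If it does, extend the sentence to that capsule, with identical wording for all patients in both arms so that blinding is unaffected.

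In the existing medication history, record use and usual clock time of these drugs, and pass this to the titrating endocrinologist with the TSH result.

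**Cost.** One sentence, one line on the card, one line on the history form and one question to the pharmacy. The downside is a slightly longer instruction and a less convenient calcium schedule. With the AM capsule at an assumed 06:00 to 08:00, calcium is allowed from 10:00 to 12:00 onward, so a breakfast dose must move. Doses at 13:00 and 18:00 (the meal times in Section 9.4) and at 22:00 still fit. If the PM capsule proves to contain LT4 and is taken at an assumed 17:30, the period 13:30 to 21:30 closes as well. Of those three times, only 13:00 and 22:00 then remain.
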